# One Month Status-Post First Treatment (Day ~30):

At the one-month follow-up visit, the patient's treated scar will be identified with the assistance of old photos and measurements, and the rectangle will be re-marked out. The patient's blood will be collected in the same manner as Day 1 and spun down in the ELMI centrifuge. The patient and blinded providers will complete the VSS and POSAS while waiting, and the scar will then be marked into 1cm squares for subsequent treatment. The two different halves of the scar will be treated with the same substance that they were in the first round by the unblinded researcher.

# Two Months Status-Post First Treatment (Day ~60):

The two-month follow-up visit will follow the same protocol as the one-month visit.

## Three Months Status-Post First Treatment (Day ~90):

The three-month follow-up visit will follow the same protocol as the one-month visit.

## Four Months Status-Post First Treatment (Day ~120):

The four-month follow-up visit will follow the same protocol as the one-month visit.

### Five Months and 1 Year Status-Post First Treatment (Day ~150 and ~ 365):

At the five-month follow-up visit the attending will obtain a 2mm punch biopsy from two sites: one from the center of the control (saline-treated) scar, and one from the center of the PRPtreated side of the scar. The biopsy sites will first be numbed with local anesthetic (after confirming the patient has no allergies to the numbing medication). After the biopsy, the site will be closed with 5-0 fast absorbing gut suture using sterile instruments in the standard sterile fashion and dressed with a band-aid. The timing of the biopsy during the visit will be after administering the VSS and POSAS.

This scar tissue specimen will be collected and stored for further examination in the laboratory setting according to the following protocol: Punch biopsies from each scar will be obtained at five months and one year. The tissue samples will then be fixed in formalin and embedded in paraffin wax. The samples will be cut and stained with hematoxylin and eosin before then receiving Masson's trichrome stain to identify collagen fibers, Verhoeff's stain to identify elastic fibers, and toluidine blue stain to identify mast cells. The density of the collagen fibers and elastic fibers will be classified as either sparse or dense, and each individual fiber will be classified as either thin or thick. Under high power view, the thicknesses of the layers in the scars compared to normal tissue using a ruler and the number of mast cells will be counted.

This study is categorized as standard risk. Autologous platelet-rich plasma has been studied extensively and has been found to be extremely safe for human use, as it is derived from the patient's own body. The most severe side effects that have been observed from PRP treatment are erythema and swelling at the application site, which subsides within 1-3 days. All patients will receive a pre-screening survey to eliminate those who meet any of our exclusion criteria that may put them at any additional risk for complications. To decrease the chance of any injectionsite-related infection, all sites will be cleaned adequately, and all procedures will be performed using proper sterile technique. Because this is an injection, the possibility of infection or minor blood vessel or nerve damage exists, but these are essentially theoretical risks, as these complications have not been observed in any studies, we are aware of. Nevertheless, in the event of any PRP-related complication, patients will have access to a team member through the clinic phone number or www.myhealthatVanderbilt.com and will be evaluated promptly. Regarding the skin biopsy, sterile technique will be used to minimize the risk of infection, and proper biopsy site closure performed by qualified persons will minimize the risk of wound breakdown. Further, 2mm punch biopsy sites are at very low risk of wound breakdown given their small size. If an infection were to occur at this site, it would be promptly treated with appropriate antibiotics and wound care.

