# Specific Aims:

(1) Compare the effectiveness of intradermally-injected autologous platelet-rich plasma versus normal saline to improve burn scars, as measured by both clinician-reported (Vancouver scar scale; VSS) and patient-reported measures (Patient and Observer Scar Assessment Scale; POSAS).

(2) Compare the effectiveness of intradermally-injected autologous platelet-rich plasma versus normal saline as a control to improve neuropathic pain associated with burn scars.

(3) Understand the mechanism of action of PRP in improving burn scars via histological analysis of collagen content in the burn scar tissue biopsy specimens.

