# 4. Inclusion/Exclusion Criteria

Inclusion Criteria:

- 18-70 years old, all sexes
- Thermal burn scar on the trunk or abdomen ≥ 1 year old that meets ONE of the following criteria:
  - Vancouver Scar Scale score  $\geq 7$
  - Patient and Observer Scar Assessment Scale (POSAS) score ≥ 35
  - Neuropathic symptoms
    - POSAS score ≥ 5 on question evaluating itchiness
    - POSAS score  $\geq$  5 on question evaluating pain

Exclusion Criteria:

- Initial burn injury was less than 1 year old
- History of chemical or electrical burn
- History of CO2 treatment to the scar of interest
- Genetic or acquired conditions that severely affect systemic wound healing or collagen formation (vasculitis, diabetes, Ehlers-Danlos syndrome, radiation therapy to the scar site or use of immunosuppressive medications within the last year, active cancer)

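### Aim 3 is about collagen content, but the amount of collagen is recorded only as an undefined two-level grade, which discards much of the information in the paired biopsies

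*Combined protocol and SAP*

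**What the plan says.** Specific Aim 3 is to understand how PRP improves burn scars "via histological analysis of collagen content in the burn scar tissue biopsy specimens".

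Section 6, under the five-month and one-year visits, takes two punch biopsies per patient: "one from the center of the control (saline-treated) scar, and one from the center of the PRPtreated side of the scar". On timing it says: "Punch biopsies from each scar will be obtained at five months and one year". Masson's trichrome is used to show collagen, Verhoeff's stain to show elastic fibres and toluidine blue to show mast cells. The readouts are:

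- **Density:** "The density of the collagen fibers and elastic fibers will be classified as either sparse or dense".
- **Fibre calibre:** "each individual fiber will be classified as either thin or thick".
- **Other:** "the thicknesses of the layers in the scars compared to normal tissue using a ruler and the number of mast cells will be counted".

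The plan does not say where sparse ends and dense begins, and does not define a per-slide summary of the thin/thick calls. The Day 1 procedures describe no biopsy. Section 10 plans 35 patients, sets significance at P<0.05 and names a Wilcoxon signed-rank test for before-and-after changes. It names no analysis for the biopsies.

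**The concern.** The aim names a quantity, collagen content. The plan stains for collagen and then records how much there is on a scale with two values. A graded fall in collagen on the PRP half that does not cross the reader's unstated cut leaves no trace in the data.

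The signed-rank test in section 10 compares before with after, so without a baseline biopsy it cannot be applied to the histology. What remains is PRP half against saline half. With a two-level grade, pairs graded dense/dense or sparse/sparse contribute nothing to that comparison.

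At stake is how a null result could be read: no effect on collagen could not be told apart from a scale too coarse to show one, although the tissue and slides might have allowed a finer reading.

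**Working it through.** **The plan's own figure.** Section 10 plans 35 patients and recruits 40 for 10% attrition. 35/(1 − 0.10) = 38.9, so 39 would do, and 40 is consistent (40 × 0.90 = 36). No power figure is given for the histology, so there is none to reproduce. I use 35 complete pairs at one biopsy time.

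**Inputs.** From the documents: 35 pairs, a 0.05 level (taken as two-sided), and one PRP and one saline specimen per patient. Assumed: the effect size, the within-patient correlation ρ and the share of saline halves graded dense.

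**Model.** Let true collagen amount be normal with SD 1 in each half, with correlation ρ and a mean lower by δ on the PRP half. The SD of the paired difference is √(2(1 − ρ)). An effect of 0.5 SD of that difference gives δ = 0.5 × √(2(1 − ρ)), which is 0.592, 0.500 and 0.387 for ρ = 0.3, 0.5 and 0.7.

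**Continuous measure.** The paired effect is 0.5 SD whatever ρ is. With 35 pairs the paired t test has 82% power and the signed-rank test about 80%. This ignores measurement error, so it is an upper figure.

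**Two-level grade, one case in full (ρ = 0.5, 90% of saline halves dense).**

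1. Φ(1.2816) = 0.90. The PRP half is dense with probability Φ(1.2816 − 0.5) = 0.783.
2. From the bivariate normal, the probability of saline dense with PRP sparse is 0.163, and of the reverse 0.046. The sum is 0.209, so 35 × 0.209 = 7.3 pairs are expected to differ.
3. The exact McNemar test needs at least 6 differing pairs: 2 × 0.5⁵ = 0.0625 is not significant, and 2 × 0.5⁶ = 0.031 is. With exactly 6, all must point the same way.
4. The chance of fewer than 6 differing pairs is 23%. Averaging the test's power over the binomial number of differing pairs gives 19%.

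**Range at 0.5 SD (exact McNemar, 35 pairs).**

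| Saline halves dense | ρ = 0.3 | ρ = 0.5 | ρ = 0.7 |
|---|---|---|---|
| 50% | 45% | 38% | 28% |
| 80% | 40% | 32% | 21% |
| 90% | 27% | 19% | 10% |
| 95% | 13% | 7% | 2% |

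**Other effect sizes (ρ = 0.5).**

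| Effect | 80% dense | 90% dense | 95% dense | Continuous (paired t) |
|---|---|---|---|---|
| 0.3 SD | 11% | 5% | 1% | 41% |
| 0.8 SD | 77% | 61% | 37% | above 99% |
| 1.0 SD | 94% | 86% | 67% | above 99% |

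**Five-level grade (0.5 SD, ρ = 0.5, signed-rank, simulated).** Power is about 71% if saline halves fall equally into the five grades, and about 74% if the cuts lie at 5%, 15%, 40% and 70% of the saline distribution. Most of the loss is recovered without image analysis, provided the grades are reasonably spread.

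**The case against.** **Sparse/dense is not the only readout.** A reader might infer that each specimen is reduced to one two-level label. That is wrong: fibres are also called thin or thick, layers are measured and mast cells are counted. The thin/thick calls could give a proportion per slide. This objection stands against the broad statement. It does not fill the gap, because calibre, layer thickness and mast cell number are not the amount of collagen, and no per-slide calibre summary is defined.

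**A ceiling at dense is not established.** A reader might infer that most halves will grade dense because entry selects severe scars, for instance through the threshold of 7 on the "Vancouver Scar Scale score". Section 4 requires only one criterion, and itch or pain alone can suffice. Nothing in the documents links the clinical scale to histological density, and with no cut-point the split could fall anywhere. This stands. But the loss does not need a ceiling: with half of saline halves dense, power is already 38% against about 80%, and at 80% dense it is 32%. The ceiling matters mainly from 90% upwards.

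**The result depends on the effect size.** A reader might infer that Aim 3 will most likely end in a finding of no difference. The documents give no expected effect, and for a large one the two-level grade performs well, as the second table shows. That prediction is therefore unsupported.

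**The aim is mechanistic.** Section 10 makes no power claim for histology, and McNemar's test is my choice for illustration. This is a fair argument for a low severity. It is not a reason to leave an inexpensive gain in information unused.

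**Conclusion.** The point holds in this form: the quantity named in Aim 3 is recorded only on a two-level scale with no cut-point, no quantitative collagen measure and no named paired analysis. At a moderate assumed effect (0.5 SD of the paired difference, 35 pairs), the two-level grade has between 2% and 45% power over the ranges examined, against at most about 80% for a continuous measure. The gap narrows as the effect grows.

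Effect size, correlation and share dense are all assumptions. The calculation also assumes a normal underlying collagen amount and complete pairs at one biopsy time. It shows that the scale is inefficient. It does not show that a ceiling exists or that the aim will fail.

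Severity is minor: Aim 3 is supportive, and Aims 1 and 2 do not depend on these grades.

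**What to change.** In section 6, under the five-month and one-year visits, make collagen area fraction (the percentage of dermal area stained as collagen) on the same Masson's trichrome slides the collagen readout for Aim 3. Fix the stain threshold, the field-selection rule and the number of fields per specimen before any slide is read. If image analysis is not available, use a five-level ordinal grade with written definitions. Keep sparse/dense as a descriptive summary.

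In section 10, state that the PRP half is compared with the saline half within each patient, at each biopsy time, by a paired signed-rank test.

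The cost is some image-analysis time, which presupposes access to digital imaging that the documents do not mention, and a threshold to settle in advance. No extra biopsy, stain or patient is needed.

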### 9. Study Withdrawal/Discontinuation

There are no anticipated circumstances under which subjects would be withdrawn from research without their consent. If subjects withdraw, there will be no penalty or consequences.

#### **10. Statistical Considerations**

-Our proposed study is methodically similar to "Treatment of traumatic scars using fat grafts mixed with platelet-rich plasma and resurfacing of skin with the 1540 nm non-ablative laser" by Cervelli et al., and we expect to analyze a similar population and outcome. In this study, they

met power with 31 patients. We will plan to enroll 35 patients, but we will recruit 40 with an expected 10% attrition.

-In our study, data will be recorded in a spreadsheet (Excel; Microsoft Corp., Redmond, WA, USA) and analyzed with SPSS software for Windows (version 15.0; SPSS, Chicago, IL, USA). Descriptive statistics will include mean ± SD for parametric variables, and median and range for nonparametric variables. The median will be used to test the difference between the groups before and after treatment, and the Wilcoxon signed rank test will be used to examine differences within groups before and after treatment. P<0.05 will be considered significant.

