# 3. Animal Studies and Previous Human Studies

# i. Cervelli, V., Nicoli, F., Spallone, D., Verardi, S., Sorge, R., Nicoli, M., & Balzani, A. (2012). Treatment of traumatic scars using fat grafts mixed with platelet-rich plasma, and resurfacing of skin with the 1540 nm nonablative laser. Clinical and Experimental Dermatology: Experimental dermatology, 37(1), 55-61.

This study in 60 human subjects found that the combination of PRP-enriched fat grafting underneath the scar along with nonablative laser resurfacing of the scar was more effective at reducing the severity of traumatic scars than either PRP-enriched fat grafting or nonablative laser resurfacing alone, as measured by the Manchester scar scale. Fat grafting is a recognized treatment to improve the appearance and feel of scars, but this study confirmed that fat grafts that are enriched with PRP also improve the appearance of scars, especially when combined with laser resurfacing. Unfortunately, this study did not directly compare the use of fat grafting without PRP to fat grafting with PRP. One drawback to fat grafting is that it frequently requires anaesthesia and operating room time in order to harvest the fat (e.g., from the abdomen or flanks), which significantly increases the time, cost and risks associated with the procedure. By contrast, when used alone, autologous PRP is fast and low-cost, can be done in the clinic, and poses minimal risk to the patient. Of note, in this study, the only side effect noted was mild transient erythema (duration of 2-3 days) and swelling (1-2 days).

# ii. Prochazka, V., Klosova, H., Stetinsky, J., Gumulec, J., Vitkova, K., Salounova, D., ... & Ocelka, T. (2014). Addition of platelet concentrate to Dermo-Epidermal Skin Graft in

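### Section 10 gives the PRP-versus-saline comparison no usable paired test, and the study it takes its sample size from does not carry over to that comparison

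*Combined protocol and SAP*

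**What the plan says.** Aim 1 is to "Compare the effectiveness of intradermally-injected autologous platelet-rich plasma versus normal saline to improve burn scars", on the VSS and POSAS. Under sections 5 and 6, one half of each patient's scar receives PRP and the other saline, the side being set by coin flip. PRP and saline results are therefore paired within patients.

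Section 10 of the combined protocol and SAP makes two statements on this point.

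- **Sample size.** It calls an earlier study methodically similar and says "we expect to analyze a similar population and outcome". That study, it says, "met power with 31 patients. We will plan to enroll 35 patients, but we will recruit 40 with an expected 10% attrition".
- **Analysis.** For the comparison of PRP with saline, the plan offers this: "The median will be used to test the difference between the groups before and after treatment". For change over time on one side, it offers this: "the Wilcoxon signed rank test will be used to examine differences within groups before and after treatment". The threshold for significance is 0.05.

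Section 10 gives no primary outcome, time point, target difference, SD or power level.

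Section 3(i) describes the earlier study: "This study in 60 human subjects found that the combination of PRP-enriched fat grafting" with laser was more effective on traumatic scars "than either PRP-enriched fat grafting or nonablative laser resurfacing alone, as measured by the Manchester scar scale". It adds: "Unfortunately, this study did not directly compare the use of fat grafting without PRP to fat grafting with PRP".

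**The concern.** Aim 1 asks whether the PRP half does better than the saline half. A before-after test within one half asks whether that half changed. Both halves can improve through time, needling, fluid injection or regression to the mean, so a significant change on the PRP half is not evidence for PRP over saline. Comparing two within-half p-values does not repair this, because one may cross 0.05 and the other miss it by chance.

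The sentence on the median is the only one that addresses the between-side question, and it does not identify a test that uses the pairing. Because the sample size is borrowed from a study with a different contrast, a reader also cannot tell what PRP-saline difference the trial could detect.

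**Working it through.** **1. The plan's own figure.** Inputs from section 10: 31, 35, 40, 10% attrition, P<0.05.

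- Attrition: 35/0.9 = 38.9, so 39 recruited would do and 40 is enough. 40 × 0.9 = 36 evaluable, at least 35. This step holds.
- The base of 31 cannot be reproduced, because no effect, SD, power or test is given. By normal approximation at two-sided 5%, d = (1.960 + 0.842)/√31 = 0.50 SD for a paired design at 80% power. For two groups totalling 31 (15.5 each) it is 2.802 × √(2/15.5) = 1.01 SD. The documents do not say which applies, if either.

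**2. The two studies side by side, from the documents.**

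| | Earlier study (section 3(i)) | This trial (sections 2, 4, 6) |
|---|---|---|
| Scars | traumatic | thermal burn, trunk or abdomen |
| Contrast | PRP-enriched fat graft plus laser, against either alone | PRP against saline |
| PRP effect isolated | no: fat graft with and without PRP not compared | yes |
| Scale | Manchester | VSS and POSAS |
| Number | 60 (section 10 cites 31) | 35 planned, 40 recruited |

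The 31 may be a subgroup of the 60; the text does not say.

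**3. What a paired test could detect.** Let D = (change on PRP half) − (change on saline half), and W = the sum of the ranks of |D| over patients with D > 0. Two-sided 5% exact limits: n = 36, reject if W ≤ 208 or ≥ 458 (size 0.0496); n = 35, W ≤ 195 or ≥ 435 (size 0.0495). Simulated power (60,000 runs, normal D without ties, mean D in units of SD(D)):

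| Mean D | n = 35 | n = 36 |
|---|---|---|
| 0.3 | 39% | 40% |
| 0.4 | 61% | 62% |
| 0.49 | 79% | 80% |
| 0.5 | 80% | 81% |
| 0.57 | 89% | 90% |
| 0.6 | 92% | 93% |

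A noncentral-t approximation with efficiency 3/π agrees. For 80% and 90% power it needs 0.50 and 0.58 SD at n = 35, and 0.49 and 0.57 SD at n = 36. Scored scales produce ties: with D rounded to whole points (assumed SD 1 to 3 points), power at a nominal 0.49 SD and n = 36 is about 78% to 80%.

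**4. What happens if within-half tests are read as the answer.** Assume no PRP effect, 36 patients, both halves improving equally by m (in SDs of change), and correlation r = 0.3 to 0.7 between halves. The documents give none of these values. Probability that the PRP half is significant and the saline half is not:

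| m | r = 0.3 | r = 0.5 | r = 0.7 |
|---|---|---|---|
| 0.3 | 0.198 | 0.169 | 0.130 |
| 0.4 | 0.194 | 0.165 | 0.128 |
| 0.5 | 0.128 | 0.113 | 0.087 |

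Over m = 0.2 to 0.5 the range is 9% to 20%. At m = 0 it is about 3% to 5%. At m = 0.8 it is about 0.4%, because both halves are then significant in about 99% of trials. The paired test on D rejects in about 5% throughout.

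**5. Whether the paired data will exist.** In section 6, the Day 1 and one-month procedures say that raters complete the VSS and POSAS, but not that they score each half. On Day 1 the patient fills out the POSAS in the waiting room and providers score once the patient is roomed. The midline is drawn later, during centrifugation. As ordered, there is no marked half to score at baseline.

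**The case against.** - **A between-group comparison is planned, and a median test is a real method.** This stands: it would be wrong to say that the plan omits the comparison. But the median test in that sense is for independent groups. It ignores the pairing, so the sentence still does not supply a suitable test.
- **Section 10 does not say that within-group tests will answer Aim 1.** True. A significant PRP half is also not a false result if that half really improved. The error arises only when it is read as PRP beating saline. With no usable between-side test, that reading is the likely fallback.
- **The 9% to 20% comes from a chosen range of improvement.** This stands too, and the values at 0 and 0.8 SD belong beside it.
- **Scoring by half is implied.** Sides are randomised Right/Left, the form for scores withholds the side, photos carry L and R, and raters are blinded. This makes separate scoring probable. The silence is a gap in wording, not evidence that halves go unscored. The Day 1 order still has to change.
- **A reader might infer that 35 patients are too few, or that 31 against 60 is a misquotation.** The documents support neither. With no target difference or SD, 35 cannot be called inadequate, and 31 could be a subgroup.

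**Conclusion.** The concern holds in this form: followed as written, section 10 cannot answer Aim 1. Its between-side sentence names no test suited to a split scar, and its one clearly named test addresses a different question. The stated power belongs to another contrast on another scale and cannot be carried over. The sample size is therefore unjustified, which is not the same as inadequate.

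The size has two parts. With 35 to 36 evaluable pairs, a paired signed-rank test has about 80% power at about 0.5 SD of the paired difference and about 90% at 0.57 to 0.58 SD, assuming near-normal differences and separate scores for each half. The penalty for relying on within-half tests depends wholly on an unknown shared improvement, as step 4 shows. The flaw in the written analysis does not depend on any of these assumed values. The change should be made before the data are analysed; the scoring part has to be settled before baseline ratings are taken, because half-specific scores cannot be recovered later.

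**What to change.** 1. In section 10, replace the sentence on the median with a primary paired analysis. For one outcome and one time point, chosen by the investigators, take the change from Day 1 on the PRP half minus the change on the saline half in each patient. Test it with the Wilcoxon signed-rank test at two-sided 0.05. Label within-half before-after tests as descriptive.
2. In section 6, state that raters and patients score each half separately at every visit. Mark the midline before the Day 1 ratings, including the patient's POSAS, so that each half has its own baseline.
3. Remove the earlier study as the power basis. State instead that 35 to 36 evaluable pairs give about 80% power for a paired difference of about 0.5 SD and about 90% for about 0.57 to 0.58 SD. Note that this assumes normal differences and that ties lower it slightly. The investigators supply the SD with its source and the smallest worthwhile difference. If that difference is below about 0.5 SD, say that power is under 80%.

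The cost is a few sentences, a reordered Day 1, and a second set of ratings per rater per visit if this is not already done. The stated basis for the sample size also becomes less favourable. None of this by itself requires more patients.

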# 5. Enrollment/Randomization

Prior to enrollment, all sixty potential study ID numbers will be randomly assigned to a treatment group (Right/Left). The randomization will be performed by coin flip (heads is right, tails is left). This will be logged in a secure REDCAP form only accessible by the researcher not conducting scar evaluations (unblinded REDCAP). There will be a secondary REDCAP form used for logging VSS/POSAS scores that does not contain this information (blinded REDCAP).

Potential candidates will be identified by the attending surgeon at the Burn Reconstruction Clinic at Vanderbilt. All patients meeting preliminary inclusion/exclusion criteria will be contacted, via phone or in person at the clinic, and given a brief description of the study. If interested in participating, inclusion/exclusion criteria will be reviewed with the patient, and the patient will be scheduled for their first appointment. Patients will be assigned to a study ID number (with associated treatment group) based on order of enrollment.

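### The analysis section specifies no paired PRP-versus-saline test for the two randomised halves of each scar

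*Combined protocol and SAP*

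**What the plan says.** Section 2 (Specific Aims) sets two comparative questions. Aim 1 is to "Compare the effectiveness of intradermally-injected autologous platelet-rich plasma versus normal saline to improve burn scars", measured by VSS and POSAS. Aim 2 compares PRP "versus normal saline as a control to improve neuropathic pain associated with burn scars".

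The design is split-scar. Under section 5, "all sixty potential study ID numbers will be randomly assigned to a treatment group (Right/Left"). In section 6 (Day 1) the scar is divided at its horizontal midpoint. At the one-month visit, and by reference at the later treatment visits, "The two different halves of the scar will be treated with the same substance that they were in the first round". Every patient therefore receives both treatments.

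Section 10 is the only analysis text. It has two sentences on testing methods in substance:
- Between groups: "The median will be used to test the difference between the groups before and after treatment".
- Within groups: "the Wilcoxon signed rank test will be used to examine differences within groups before and after treatment".

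The significance level is 0.05, with sidedness not stated. No other section gives an analysis method.

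**The concern.** The aims ask whether the PRP half does better than the saline half of the same scar. The plan gives no test that answers this with the pairing kept.

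Three analyses could claim to follow the text: an unpaired test between halves, separate before/after tests in each half, or a paired test of the difference. They can disagree. An unpaired test discards the main benefit of a split-scar design, which is that differences between patients cancel. Separate before/after tests do not compare the treatments: both halves can improve significantly when PRP is better, and one half can cross 0.05 while the other narrowly misses it when PRP does nothing.

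**Working it through.** **Sample size.** 35/(1 − 0.10) = 38.9, so 39; the plan recruits 40, and 40 × 0.90 = 36. The figures agree to within a patient or so. The power basis, 31 patients in a cited study, cannot be reproduced, because no effect size, SD, power level or test is given. I use n = 35.

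**Which sentence answers which question.**

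| Question | Method in section 10 | Does it compare PRP with saline within patient? |
|---|---|---|
| PRP versus saline (aims 1 and 2) | The median | No: a summary, or at best an unpaired test |
| Before versus after in one half | Wilcoxon signed-rank | No: paired in time, one treatment only |

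**What the pairing is worth.** Assume that each half's change has SD 1 and that the two changes have correlation ρ. Then D = (PRP change) − (saline change) has SD √(2(1 − ρ)). For a PRP advantage of 0.5 SD, the standardised paired effect is 0.5/√(2(1 − ρ)):
- ρ = 0.3: 0.5/1.183 = 0.42
- ρ = 0.5: 0.5/1.000 = 0.50
- ρ = 0.7: 0.5/0.775 = 0.65

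At two-sided 5% and 80% power, 35 pairs detect (1.96 + 0.84)/√35 = 0.47, or 0.47/√0.955 = about 0.49 after allowing for signed-rank efficiency. Power should therefore be below 80% at ρ = 0.3, near 80% at 0.5 and well above it at 0.7.

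**Simulation, true PRP advantage.** Normal changes, n = 35, shared improvement 0.5 SD plus a further 0.5 SD for PRP, 2,000 runs per setting:

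| ρ | Signed-rank on D | Unpaired rank test | Median test (no continuity correction) |
|---|---|---|---|
| 0.3 | 66.4% | 52.7% | 38.8% |
| 0.5 | 79.4% | 54.3% | 39.6% |
| 0.7 | 95.5% | 54.1% | 35.6% |

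With the continuity correction, median-test power falls to as low as about 16% (ρ 0.5 to 0.7, n = 35 or 36). In the same setting only the PRP half was significant in 19% to 20% of runs. The PRP half was significant in essentially all runs, so both halves were significant in about 80%, and the within-half tests then show no distinction.

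**Simulation, no PRP effect.** Percentage of runs in which the PRP half is significant before/after and the saline half is not:

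| ρ | Shared change 0.2 SD | 0.34 SD | 0.5 SD |
|---|---|---|---|
| 0.3 | 14.1% | 20.4% | 13.2% |
| 0.5 | 11.4% | 17.5% | 11.2% |
| 0.7 | 8.8% | 14.0% | 11.1% |

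With no shared change the figure is about 4%, and at 0.8 SD it is under 1%. The paired test rejected in 4.2% to 5.4% of runs in either direction, so it wrongly favours PRP in about 2.5%. Under no effect the unpaired rank test rejected in 0% to 2.6% and the median test in 0.5% to 3.4%: both are conservative.

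**The case against.** **The between-group sentence may be a slip for the median test.** This is the kindest reading, and it makes the sentence a recognised test. It does not supply a paired one: the median test is for independent samples.

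**A reader might infer that the trial will claim efficacy from a significant PRP half beside a non-significant saline half.** The documents do not support that. Section 10 states a separate between-group comparison, however loosely, and nowhere says that the within-half results decide the question. The 9% to 20% figures are conditional on that misuse.

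**A reader might also infer that an unpaired test would produce false positives.** It would not. With positively correlated halves it is conservative, and the cost is power.

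**The size is assumed throughout.** This stands. The gain from pairing is large at ρ = 0.7 and modest at 0.3, and it disappears at zero correlation (about 51% for both the paired and the unpaired rank test). The unpaired rank test is a benchmark; section 10 does not name it.

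**Half-level scores may already be intended.** Section 5 suggests it: "There will be a secondary REDCAP form used for logging VSS/POSAS scores that does not contain this information", which keeps the assigned side from those who score. At follow-up "the rectangle will be re-marked out" before scoring, but the rectangle encloses the whole scar. On Day 1 the scores are described before the midline is drawn. The documents therefore show neither that halves are scored separately nor that they are not. Without half-level scores D cannot be computed, so this must be settled before the test can be used.

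**Conclusion.** The point holds on the text: no paired PRP-versus-saline test is specified for a design that randomises the halves of one scar. This should be corrected before analysis, because section 10 is the only inferential text for the main question.

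If the between-group sentence is carried out as an unpaired test, the consequence is lost power: about 52% to 55% for a rank test, and less for the median test, against about 66% to 95% for the paired test. This assumes normal changes, 35 patients, a 0.5 SD advantage and correlation 0.3 to 0.7. Excess false claims (roughly 9% to 20%, against about 2.5%) would arise only if conclusions were taken from the within-half tests and the shared change were about 0.2 to 0.5 SD. The conclusion rests on the wording of the plan, not on any of these assumed values.

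**What to change.** **Section 10, VSS and POSAS (including the itch and pain items).** Replace the between-group sentence with:

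> For each patient compute D = (change from baseline in the PRP half) minus (change from baseline in the saline half). PRP versus saline is tested by a two-sided Wilcoxon signed-rank test of D at P<0.05. Before/after change within each half is descriptive only.

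**Section 10, biopsy measures (aim 3).** Biopsies are taken only at five months and one year, so there is no baseline and D does not apply. Add a within-patient comparison of the two halves at each biopsy time: signed-rank for mast-cell counts and layer thicknesses, and McNemar or sign test for sparse/dense and thin/thick. Thin/thick is recorded fibre by fibre, so one value per half must be defined first.

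**Section 6, precondition.** State that the VSS and POSAS used in the analysis are scored separately for the left and right half at every visit. State also that the analysis baseline is taken after the midline is marked and before injection, and is kept distinct from the whole-scar eligibility score.

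Primary outcome, visit and handling of the two raters remain separate decisions for the sponsor; this wording does not settle them.

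**Cost.** The analysis change is a few sentences, uses a test already named, and needs no extra patients or visits. If halves are not already scored separately, it also needs a left/right field on the blinded forms, some scoring time at each visit and a change to the Day 1 order. For patients already scored on the whole scar only, a half-level baseline cannot be recovered.
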